## 2. Introduction

### Background and rationale:

The CASTLE study is a randomised trial to assess impact of digital chest X-ray with computer aided diagnosis (DCXR-CAD) on TB treatment initiation and inpatient mortality among people living with HIV admitted to hospital. Please refer to the study protocol for further information.

This document outlines how data will be analysed.

## 3. Study Methods

### Trial design

CASTLE is a cluster randomised trial with two trial arms. Clusters are day of admission to hospital.

Arm 1 Usual Care alone	Any TB diagnostic tests standardly available at Zomba central hospital, on treating clinician request. Includes sputum Xpert, urine AlereLAM and conventional plain film CxR, if requested.
Arm 2 Interventions (DCXR-CAD + FujiLAM + usual care)	FujiLAM + AlereLAM + DCXR-CAD for everyone (regardless of symptoms). Study team members will arrange sputum Xpert if CAD score $\geq 60$ . This is in addition to usual care (as above)

CASTLE has a third arm which is a nested observational diagnostic cohort (“diagnostic cohort”).

People admitted on days assigned to diagnostic cohort arm do not contribute to trial outcomes.

The overall allocation ratio is 4:4:1 to usual care : interventions : diagnostic cohort. Accordingly, there is equal allocation (4:4) to the two trial arms.

### Randomisation

Randomisation codes were generated randomly using block randomisation with varying randomly assigned block sizes (blocks could be 9, 18 or 27 days).

R statistical software with package “RandomizerR” was used to generate sequences using the following code:

```
a <- rpbrPar(300,rb=c(9,18,27), K=3, ratio=c(4,4,1), groups=c("usual","CXR+LAM","cohort"))
b <- genSeq(a,50,220188) # includes a seed
c <- getRandList(b)
d <- t(c)
```

Fifty separate sequences were generated using above code (by [name]) and exported to a spreadsheet. A second academic researcher (not affiliated with the CASTLE study) chose one of the fifty sequences and co-ordinated the printing of allocation codes and putting each cluster (day) allocation into sequentially numbered, sealed, opaque envelopes.

Each morning, the CASTLE trial team open the next sealed envelope in the sequence to reveal the allocation for that day.

[figure not shown]
### Sample size

We plan to recruit 102 clusters per trial arm.

Sample size was calculated for primary outcome (TB treatment initiation). We assumed 10% people in usual care arm would initiate TB treatment by the time of hospital discharge, and 18% of people in intervention arm would initiate TB treatment. We assumed clusters with three participants per cluster and minimal clustering of outcome (ICC of 0.005).

[figure not shown]
Sample size for primary outcome was calculated in R using 'clusterPower' package

```
library(clusterPower)
p_int <- c(0.12,0.14,0.16,0.18,0.20,0.22)
pwr_3 <- crtpwr.2prop(alpha = 0.05, power = NA, m = 102, n = 3, cv = 0.1, p1 = p_int, p2 = 0.1, icc =
0.005, pooled = FALSE, p1inc = TRUE)
```

Sample size for secondary outcome was calculated in stata using below command (assuming 80% survival by 56 days):

```
power logrank 0.8, k1(102) m1(3,4) hratio(0.6,0.65,0.7,0.75,0.8) rho(0.005) cvcluster(0.05)
```

If there were three participants per cluster, K 0.005 and TB treatment initiations 10% in usual care and 18% in intervention arm, then with 102 clusters per arm we will have 81% power to detect a difference between arms at least that large.

For secondary (survival) outcome, if there are four people per cluster and a hazard ratio of 0.6 (ICC 0.005 and survival probability 80% in usual care group) then with 102 clusters per arm we could have 81.6% power to detect an effect at least that large. With three people per cluster the power drops to 69.9%.

## Framework

The hypothesis for CASTLE is that DCXR-CAD plus FujiLAM plus usual care is superior to usual care alone.

## Statistical interim analyses and stopping guidance

There are no planned interim analyses.

## Timing of final analysis

Final analysis will be conducted when the final participant has completed 56 days from time of enrolment.

#### **Timing of outcome assessments**

The primary outcome (TB treatment initiation) will be assessed at the time the participant is discharged from hospital (including TB treatment started on the day of discharge), participant dies or at 56 days from enrolment, whichever is the earlier.

The secondary outcomes are: TB treatment initiation within 24 hours from enrolment in trial, measured up to 24 hours from enrolment; undiagnosed TB at the time of discharge from hospital, measured at the time participant is discharged from hospital or dies or 56 days from enrolment whichever is earlier; and time-to-death, measured up to 56 days from enrolment.

## **4. Statistical Principles**

### **Confidence intervals and *p* values**

All applicable statistical tests (*p* values) will be two-sided. All confidence intervals will be 95% and will be two sided.

There is a single primary outcome and three secondary outcomes. No adjustments for multiplicity are planned.

### **Adherence and protocol deviations**

Adherence to intervention is defined as receiving a DCXR and urine LAM test (for those in intervention arm). Analysis is intention-to-treat and is not affected by adherence to intervention.

Protocol deviations are defined in LSHTM-SOP-012-02 (LSHTM Research Governance and Integrity Office, 2019-11-28). Major and minor protocol deviations and any protocol violations will be summarised in an appendix to main trial paper.

### **Analysis populations**

CASTLE will be analysed on an intention to treat basis.

The analysis population will include all randomised participants according to the intervention their cluster was randomised to receive, regardless of whether the intervention was received or not.

Participants enrolled into a randomised cluster who were subsequently found to be ineligible for the CASTLE trial will be removed from analysis.

Should there be a major protocol deviation / violation involving large numbers of participants not receiving the intervention to which their cluster was assigned, we would consider a per protocol additional analysis.

## 5. Trial Population

### Screening data

The following summaries will be presented for all screened potential participants:

Number of days recruiting, number of potential participants screened, number of screened potential participants not recruited and the reason for non-recruitment.

### Eligibility

Eligibility for CASTLE is detailed in the protocol.

Inclusion:	Adult (age $\geq 18$ years), admitted to medical ward at Zomba Central Hospital (for any reason), HIV positive (new diagnosis or known diagnosis)
Exclusion:	Unable or unwilling to consent, already on TB treatment or has received TB treatment in past six months, admitted for longer than 18 hours at the time of start of assessment for CASTLE enrolment.

### Recruitment

A “CONSORT” diagram will be used to summarise the number of people screened, eligible, consented, randomised, receiving their allocated intervention and withdrawing / lost to follow up.

### Withdrawal / follow up

Should any participant withdraw from the study, this will be described, including the level of consent withdrawal (i.e. consent withdrawal for any or all of intervention, for follow up or for data retention). The reasons for withdrawal (where stated by participant) will be captured.

For participants who are lost to follow up by 56 days, they will be censored from follow up at the last time they were observed alive by the study time (this will usually be date of discharge from hospital) or the last time a reliable witness reports observing the person alive.

### Baseline participant characteristics

Baseline participant characteristics for categorical variables will be summarised by frequencies and percentages. Continuous data (age, CD4 count) will be summarised by median and interquartile range. Tests of statistical significance will not be undertaken for baseline characteristics; rather the clinical importance of any imbalance will be noted.

The primary analysis will be unadjusted for baseline characteristics. If there is a major imbalance in baseline characteristics, we would consider a secondary sensitivity analysis adjusted for the imbalanced variable.

## 6. Analysis

### Outcome definitions

	Definition	Timing	Notes
Primary outcome			
1. Proportion of people starting TB treatment	Participant started on TB treatment. Numerator is all those starting TB treatment and denominator is all those enrolled.	From time of enrolment in CASTLE trial to end of the day in which a participant was discharged from hospital, or time participant died, or 56 days from enrolment in CASTLE whichever is sooner.	TB treatment as recorded in Zomba Central hospital TB register (paper-based ledger). Every participant's name checked against TB register within a week of discharge. Includes people started on TB treatment even if TB treatment subsequently stopped. Includes TB treatment started on the same day as discharge from hospital.
Secondary outcomes			
2. Mortality (time to event)	Death from any cause	From time of enrolment in CASTLE trial to 56 days from enrolment. For those who are not reached at or after 56 days, their time in trial will be censored at the time of death or time they were last known to be alive by a reliable witness.	Includes in hospital deaths and deaths after discharge from hospital up to 56 days from enrolment. Deaths reported by relatives, mainly phonecall based tracing and home visits if unable to contact by phone. If a person dies on the same day as enrolment they will be assigned 0.5 of a day survival time.
3. Proportion starting same day TB treatment.	TB treatment started within 24 hours of enrolment in CASTLE trial.	Measured from time of enrolment in CASTLE for further 24 hours.	Time of starting TB treatment is time that guardian picks up TB medicines from TB office at Zomba Central Hospital (or ward nurse picks up medicines if no guardian). Time of picking up TB medications determined by observation of study team and guardian / relative / patient / nurse report (as time is not recorded in paper ledger, only date).
4. Proportion with undiagnosed TB.	Sputum culture at mycobacterial lab in Blantyre grows M. tuberculosis complex organisms and participant did not start TB treatment at or before time of discharge from hospital or death or 56 days from enrolment (whichever is sooner).	TB treatment initiation as defined in primary outcome.	People whose sputum grows non-tuberculous mycobacteria are not included as having undiagnosed TB. People who start TB treatment but who subsequently interrupt TB treat are not treated as having undiagnosed TB. Denominator is all people in CASTLE trial, not just those who produce sputum.
Other outcomes / measurements			
Inpatient mortality	Death from any cause	From time of enrolment until time of hospital discharge or 56	Determined through observation, notes review, asking healthcare staff and the ward paper ledger.

		days from enrolment, whichever is sooner.	
56 day mortality (measured as a proportion)	Death from any cause	From time of enrolment in CASTLE trial to 56 days from enrolment. Analysed as binary data.	In hospital deaths determined as above, deaths after discharge from hospital ascertained from phone-call with nominated next of kin.
Microbiologically confirmed TB.	Proportion of all TB diagnoses that are microbiologically confirmed.	Refers to TB diagnoses made before discharge from hospital or before 56 days from enrolment, whichever is sooner.	Microbiologically confirmed means at least two positive Acid Fast Bacilli (AFB) smears or one or more Xpert Mtb/Rif positive or one or more culture positive for M. tb on any specimen or a positive urine LAM result. Includes samples collected by CASTLE team and those by usual care team.
Intervention fidelity	Proportion of people recruited in intervention clusters who have a CxR with CAD score and urine LAM result recorded	We will record any instance where intervention not delivered on the same day as enrolment.	Reasons for not receiving interventions will also be detailed.

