### Analysis methods

	Metric to be reported	Method of calculation
Primary outcome		
1. TB treatment initiation	Risk ratio of TB treatment initiation by allocation arm.  We will also calculate and report absolute risk difference.	Regression using robust standard errors to account for clustering. GLM with log-link and binomial distribution to approximate risk ratio.*  Absolute risk difference will be obtained from binomial GLM with identity link function.

Secondary outcomes		
2. Mortality	Hazard ratio for death (time to event)	Cox regression using robust standard errors to account for clustering.
3. Same day TB treatment initiation	Risk ratio of TB treatment initiation within 24 hours from enrolment by allocation arm.	Regression using robust standard errors to account for clustering. GLM with log-link and binomial distribution to approximate risk ratio.*
4. Undiagnosed TB	Risk ratio of undiagnosed TB by allocation arm.	Regression using robust standard errors to account for clustering. GLM with log-link and binomial distribution to approximate risk ratio.*

Other outcomes		
5. Inpatient mortality	Risk of death prior to discharge from hospital.	Regression using robust standard errors to account for clustering. GLM with log-link and binomial distribution to approximate risk ratio.*
6. 56 day mortality (measured as a proportion)	Risk of death within 56 days from enrolment (i.e. analysed as a proportion rather than time to event)	Regression using robust standard errors to account for clustering. GLM with log-link and binomial distribution to approximate risk ratio.*
7. Microbiologically confirmed TB.	Proportion of TB	Numerator is those with microbiologically confirmed TB and denominator is all who had TB diagnosed.
8. Intervention fidelity	Proportion	Numerator is all those who received DCXR with valid CAD score and a FujiLAM urine result, denominator is all those recruited in clusters allocated to intervention arm.

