## Missing data

No imputation will be performed for missing data. There will be no missing data for day recruited or cluster (i.e. arm) allocation. If an outcome is missing then it will be reported as such and not imputed.

No adjustment by baseline variables is planned, therefore missing data other than randomisation arm and outcome does not affect analysis. There is no imputation for missing covariates at baseline.

For the mortality secondary outcome (time to event), participants will be censored at the time they were last known to be alive.

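### The time-to-death row of the SAP names death, the event of that outcome, as a censoring time for people not reached at day 56

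*SAP*

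**What the plan says.** The table under Outcome definitions (SAP section 6) gives secondary outcome 2 as all-cause mortality, analysed as time to event over 56 days from enrolment. Its Timing cell then deals with participants who are not contacted at day 56 or later, and says that "their time in trial will be censored at the time of death or time they were last known to be alive", with a reliable witness as the source.

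The Notes cell of the same row treats deaths as outcomes. On scope it says "Includes in hospital deaths and deaths after discharge from hospital up to 56 days from enrolment". On ascertainment it says "Deaths reported by relatives, mainly phonecall based tracing and home visits if unable to contact by phone". On very early deaths it says "If a person dies on the same day as enrolment they will be assigned 0.5 of a day survival time".

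The censoring rule appears in two other places. Under Withdrawal / follow up, for people lost by day 56, "they will be censored from follow up at the last time they were observed alive by the study time", or when a reliable witness last reported seeing them alive. Under Missing data, for this same outcome, "participants will be censored at the time they were last known to be alive". Neither lists death as a censoring time.

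Timing of outcome assessments describes the outcome as "time-to-death, measured up to 56 days from enrolment", and the Analysis methods table reports a hazard ratio for death from a Cox regression with cluster-robust standard errors.

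**The concern.** A Cox model needs two things for each person: a time, and an indicator of whether that time ended in the event or in censoring. The Timing cell gets the time right, since observation does stop at death, but attaches the wrong status to it. A programmer who follows it to the letter would set the indicator to censored for a participant who was not reached at day 56 but is known to have died.

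The clause is aimed at a group in which deaths can occur. Someone who has died cannot be contacted in person, and post-discharge deaths are learned from relatives. The SAP does not say whether a relative's report means that the participant was reached. If it does not, those reported deaths fall under the clause. The separate binary 56-day mortality outcome would still count them, so the two mortality analyses could disagree about who died.

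**Working it through.** **1. The three statements of the rule, side by side**

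| Place in the SAP | Who | Censored at | Death listed? |
|---|---|---|---|
| Outcome definitions, outcome 2, Timing cell | not reached at day 56 or later | death, or last known alive | yes |
| Withdrawal / follow up | lost to follow-up by day 56 | last observed alive by the study or by a reliable witness | no |
| Missing data | time-to-event mortality | last known alive | no |

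The outcome table is the odd one out.

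**2. What the row intends**

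The Definition cell makes all-cause death the event. The Notes cell counts in-hospital deaths, post-discharge deaths and deaths reported by relatives, and gives a same-day death half a day of survival time. The outcome is named as time to death, and the estimate is a hazard ratio for death. Every one of these treats a known death within 56 days as an event.

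**3. Does any planned figure depend on the clause?**

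Inputs from the Sample size section: usual-care survival 0.8, hazard ratio 0.6, 102 clusters per arm, 3 or 4 people per cluster, ICC 0.005, cluster-size CV 0.05. Two-sided alpha of 0.05 is assumed, because the log-rank command states none.

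- Intervention survival: 0.8^0.6 = 0.8747.
- Expected deaths, E = n per arm × [(1 − 0.8) + (1 − 0.8747)]. Three per cluster: 306 × 0.3253 = 99.5. Four per cluster: 408 × 0.3253 = 132.7.
- Design effect, DE = 1 + [(1 + 0.05²) × m − 1] × 0.005. m = 3: 1.0100. m = 4: 1.0151.
- Freedman log-rank power = Φ{√(E/DE) × (1 − 0.6)/(1 + 0.6) − 1.96}. m = 3: 69.9%. m = 4: 81.6%.

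Both match the SAP. The calculation counts every expected death as an event, so it already follows the evident intent, and correcting the clause leaves it unchanged.

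**4. Size under a literal coding**

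This would need the share of deaths that occur in people counted as not reached, by arm. The SAP gives no such share and does not define being reached, so no loss of power or shift in the hazard ratio can be derived from it.

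**The case against.** The strongest reply is that the document resolves the matter itself. The phrase is in the Timing column, which says when a person's time in the trial ends, and on that reading both listed dates are right and only the verb is loose. The Definition cell is correct. A literal reading would contradict the Notes cell, the name of the outcome, the hazard ratio for death and the Missing data section. It is also possible that no known death falls under the clause: post-discharge deaths are learned by contacting relatives or next of kin, and inpatient deaths from observation, notes, staff and the ward ledger, so those participants may all count as reached.

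Most of this stands, and it keeps the point minor. It does not make the sentence correct. A plan should fix the event indicator without leaving the programmer to infer it, and the outcome table is where a programmer will look.

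A reader might go further and infer that the trial plans to discard deaths, or that the survival analysis will lose power or give a biased hazard ratio. The documents do not support that. The same row counts those deaths, and any size put on the loss would rest on a miscoding share with no source in the SAP. Nor is there anything to suggest that miscoding would differ between arms.

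**Conclusion.** The clause is wrong as written and conflicts with two other statements of the censoring rule in the same document. It is a wording error in the Timing cell of a secondary outcome. The choice of model, event and follow-up window is not in question. Under the evident intent the effect is nil, and the stated power of 69.9% or 81.6% is unaffected. Under a literal coding some known deaths could become non-events, but possibly none would, and the number cannot be determined from the SAP. The conclusion rests on reading the outcome row as a whole together with the Withdrawal / follow up and Missing data sections; the power check adds only the assumed alpha. Severity: minor.

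**What to change.** In the Timing cell for secondary outcome 2, delete the first of the two censoring alternatives (*the time of death or*). Then state the rule in full:

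- a known death from enrolment up to day 56 is an event on its date;
- a person known to be alive at day 56, including one who dies later, is censored at day 56;
- everyone else is censored at the time last known to be alive, as in Withdrawal / follow up and Missing data.

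The middle line is needed because the SAP foresees contact after day 56. A rule that only separated known deaths up to day 56 from people not known to have died would leave a death on, say, day 60 as neither event nor censored. It would also censor someone reached alive on day 70 beyond the 56-day window.

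The cost is one phrase deleted and a short rule added. No new data or analysis is needed.

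### Does counting untreated participants without a sputum culture as non-events undermine the undiagnosed-TB comparison?

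*SAP*

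**What the plan says.** In the Outcome definitions table of the SAP, undiagnosed TB has two parts. The first is "Sputum culture at mycobacterial lab in Blantyre grows" organisms of the *M. tuberculosis* complex. The second is that no TB treatment was started by discharge, death or day 56, whichever came first. The note on the denominator reads "Denominator is all people in CASTLE trial, not just those who produce sputum". The Analysis methods table gives the measure as "Risk ratio of undiagnosed TB by allocation arm", from a log-binomial model with robust standard errors.

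Three other places bear on the point:

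- **Trial design.** In the intervention arm, "Study team members will arrange sputum Xpert if CAD score" is 60 or more. This concerns Xpert, not culture.
- **Randomisation.** The team is aware of the day's allocation: "Each morning, the CASTLE trial team open the next sealed envelope in the sequence to reveal the allocation for that day".
- **Intervention fidelity (Analysis methods, item 8).** A coverage proportion is planned for the intervention's own tests: "Numerator is all those who received DCXR with valid CAD score and a FujiLAM urine result". No matching count is planned for culture.

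The Missing data section says that missing outcomes are reported as missing and not imputed.

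**The concern.** An untreated participant who gave no sputum, or whose culture gave no usable result, cannot be an event but stays in the denominator. That person is scored like someone with a negative culture. Two things then seem to follow: each arm's proportion is too low as a measure of undiagnosed TB, and the risk ratio mixes the effect of the intervention with any difference between arms in how often culture finds untreated cases.

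Sputum work-up differs by arm and the team knows the allocation, so equal yield is not guaranteed. The intervention could also change who is left untreated. If it leads mainly sputum producers to treatment, the remaining cases are harder for culture to see. None of the planned outputs (flow diagram, baseline table, fidelity measure, per-protocol sensitivity analysis) would show culture availability by arm. At stake is how one of three secondary outcomes is interpreted.

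**Working it through.** **Inputs from the SAP (Sample size).** 102 clusters of 3 per arm, so 306 per arm; ICC 0.005; treatment started in 10% (usual care: "We assumed 10% people in usual care arm would initiate TB treatment by the time of hospital discharge") and 18% (intervention). The SAP gives no event rate, culture yield or power for outcome 4, so every such value below is assumed.

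**The plan's own figure.** The design effect, with the coded cv of 0.1, is 1 + ((0.1² + 1) × 3 − 1) × 0.005 = 1.01015. The standard error is √[1.01015 × (0.18 × 0.82 + 0.10 × 0.90) / 306] = 0.0280. Power is Φ(0.08/0.0280 − 1.96) = 81.5%, against 81% stated. The planned size therefore reproduces.

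**1. What unequal yield does.** Let *y* be the probability that an untreated TB case has a positive culture, with no false positives. Then observed risk = true risk × *y*, and

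observed RR = true RR × (*y*₁ / *y*₀), with 1 = intervention and 0 = usual care.

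| Assumed yield, intervention vs usual care | Factor on RR |
|---|---|
| equal | 1.00 |
| 60% vs 50% | 1.20 |
| 50% vs 60% | 0.83 |
| same coverage, culture sensitivity 70% vs 80% | 0.88 |

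**2. Yield can differ without any difference in collection.** Assume 12% have TB (36.72 of 306 per arm), half of them produce sputum (18.36), and culture detects every producer.

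- Usual care treats 40% of all cases: untreated 36.72 × 0.6 = 22.03, of whom culture sees 18.36 × 0.6 = 11.02.
- The intervention treats 70% of producers and 50% of non-producers: untreated 5.51 + 9.18 = 14.69, of whom culture sees 5.51.
- True RR = 14.69/22.03 = 0.67; observed RR = 5.51/11.02 = 0.50.

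**3. Would a coverage table settle it?** No. Suppose half of all participants in each arm have a valid culture, but yield among untreated TB cases is 40% (intervention) and 50% (usual care). A true RR of 1.00 is then seen as 0.40/0.50 = 0.80, although coverage looks identical. The condition that matters concerns untreated TB cases, who cannot be identified without the missing cultures.

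**4. Would a sensitivity analysis change a conclusion?** Assume 5 and 8 events among 306 per arm. RR = 5/8 = 0.63. SE(log RR) = √(1/5 + 1/8 − 2/306) = 0.564, so the 95% interval (the level the SAP sets) is 0.21 to 1.89. A design effect of 1 + (3 − 1) × 0.005 = 1.01 moves the upper limit only to 1.90.

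Untreated: 306 × 0.82 = 250.9 and 306 × 0.90 = 275.4. With 50% coverage, 125.5 and 137.7 are cultured, with positivity 4.0% and 5.8%. Then:

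- uncultured in both arms at their own arm's positivity: 10/16 = 0.63, unchanged;
- coverage 50% (intervention) vs 60% (usual care): (5/0.5)/(8/0.6) = 10/13.33 = 0.75;
- one arm's uncultured at zero, the other's at its own positivity: 5/16 = 0.31 and 10/8 = 1.25, which are simply RR × 0.5 and RR / 0.5;
- RR reaches 1.00 with 3 hidden cases in the intervention arm and none in usual care (3/125.5 = 2.4%), or with 11 if usual care is at its own positivity (11/125.5 = 8.8%).

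All of these values lie inside the interval of 0.21 to 1.89, which already allows no effect.

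**The case for a change.** The strongest case for a change is that the SAP plans coverage figures for the intervention's tests but none for the test that defines a secondary outcome. A label such as culture-confirmed untreated TB, a small table by arm and one supportive analysis would cost little, use data already in hand, and avoid a choice of method after the results are known.

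Part of this stands. The short name of the outcome promises more than culture can deliver, and a reader will want the number of valid cultures by arm. But the definition sits in the same table row as the name, so anyone reporting the outcome must describe it as culture growth without treatment. Counting the cultures is what an analyst does when tabulating such an outcome.

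The rest does not stand. The two features cited for unequal yield are weak: one concerns Xpert, and knowledge of the allocation applies to any outcome the team collects. How sputum for culture is obtained is a matter for the protocol, which is not at hand. The obvious alternative, a denominator of people with a culture result, would select on something that happens after randomisation and is worse. The proposed supportive analysis cannot test the condition it is meant to address.

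One small ambiguity remains. The denominator note speaks of people who do not produce sputum, and does not say whether a lost or contaminated specimen is a non-event or falls under the missing-outcome rule. Analysts can settle that in a footnote.

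**Conclusion.** No change to the plan is called for. The SAP states its numerator, its denominator and its handling of people without sputum openly. For that defined outcome the risk ratio among all enrolled is a valid intention-to-treat comparison. It is a fair trade-off: some understatement of the true burden in return for keeping the groups as randomised.

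Two cautions belong in the interpretation. The proportions are lower bounds on undiagnosed TB if positive cultures are not false. The ratio describes the effect on all undiagnosed TB only if yield among untreated cases is equal by arm, which the SAP neither shows nor contradicts. The possible distortion is the ratio of the two yields, for example 0.83 to 1.20 for 50% and 60%. These yields are assumptions, so neither the size nor the direction of any bias can be derived from the SAP.

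Stating the number of valid cultures by arm is ordinary good reporting, with the reminder that equal coverage does not prove equal yield. With event counts as low as those assumed here, added sensitivity analysis brings no gain. The primary outcome does not depend on culture and is untouched.

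### As written, the binary 56-day mortality analysis drops participants of unknown day-56 status, mostly people discharged alive, so its sample is selected on part of the outcome

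*SAP*

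**What the plan says.** Among the other outcomes in section 6, Outcome definitions, 56-day mortality measured as a proportion runs "From time of enrolment in CASTLE trial to 56 days from enrolment. Analysed as binary data". Analysis methods, item 6, assigns it a GLM with log link, binomial distribution and robust standard errors.

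The two parts of this outcome are found in different ways:

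- Inpatient deaths: "Determined through observation, notes review, asking healthcare staff and the ward paper ledger".
- Later deaths: "deaths after discharge from hospital ascertained from phone-call with nominated next of kin".

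On unknown outcomes, the Missing data section says: "If an outcome is missing then it will be reported as such and not imputed". Its censoring rule names one analysis only: "For the mortality secondary outcome (time to event), participants will be censored at the time they were last known to be alive". Withdrawal / follow up adds that, for those lost, the last sighting alive "this will usually be date of discharge from hospital".

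The primary outcome has an explicit denominator: "Numerator is all those starting TB treatment and denominator is all those enrolled". Undiagnosed TB and items 7 and 8 of Analysis methods also have one. The 56-day mortality proportion has none, and no rule for participants whose day-56 status is unknown.

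**The concern.** A binomial GLM has no censoring. A participant with no day-56 status and no imputed value simply leaves the model. That loss is tied to the outcome: inpatient deaths need no tracing and are kept, while the people removed have mostly survived the admission. Their survival to discharge is recorded and used in the Cox model, but is discarded here.

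This item is the SAP's planned 56-day risk of death. If tracing succeeds to different degrees in the two arms, its risk ratio can move away from 1 with no true effect. It can then differ from the hazard ratio in the same participants purely because missing data are handled differently.

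**Working it through.** **Inputs.** The 20% risk of death by day 56 comes from Sample size (80% survival). The SAP gives neither the untraced share nor the inpatient share of deaths, so both are assumed and varied.

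**The plan's own figure.** The 80% survival sits behind the stated survival power, which reproduces with Freedman's formula.

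- Design effect = 1 + [(1 + 0.05²)m − 1] × 0.005, which is 1.01505 for m = 4 and 1.01004 for m = 3.
- Events = (102m / design effect) × [0.20 + (1 − 0.8^0.6)] = 130.8 for m = 4 and 98.6 for m = 3.
- Power = Φ(√events × 0.4/1.6 − 1.96) = 81.6% and 69.9%, as stated.

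**Complete-case risk.** Let I be the risk of inpatient death, P the risk of later death (I + P = 0.20), and u the untraced share of those discharged alive. If the untraced die after discharge at the traced rate:

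reported risk = [I + P(1 − u)] / [1 − (1 − I)u]

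| u | I = 0.10, P = 0.10 | I = 0.15, P = 0.05 |
|---|---|---|
| 5% | 0.195/0.955 = 20.4% | 0.1975/0.9575 = 20.6% |
| 10% | 0.190/0.910 = 20.9% | 0.1950/0.9150 = 21.3% |
| 15% | 0.185/0.865 = 21.4% | 0.1925/0.8725 = 22.1% |
| 20% | 0.180/0.820 = 22.0% | 0.1900/0.8300 = 22.9% |

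**Risk ratio with no true effect.** With 15% untraced in one arm and 5% in the other, the ratio is 21.39/20.42 = 1.05 (I = 0.10) or 22.06/20.63 = 1.07 (I = 0.15). It falls below 1 if the arms are swapped. With equal tracing it is 1.00.

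**Risk ratio with the SAP's hazard ratio of 0.6.** The true ratio is (1 − 0.8^0.6)/0.20 = 0.627. With 5–20% untraced equally in both arms, and inpatient deaths at 10–12% in usual care and scaled with total risk in the other arm, the complete-case ratio is 0.628–0.633. That is almost no distortion.

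**When the sign changes.** The 20% is a weighted average of the included and the excluded, so the bias is zero exactly when the untraced have a 20% risk of dying after discharge. With 10% untraced, that is 1.6, 2.0, 2.5 and 4.6 times the traced rate for I = 0.08, 0.10, 0.12 and 0.15.

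Take I = 0.08, u = 0.10 and the untraced dying at twice the traced rate:

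- Traced post-discharge risk = (0.12/0.92)/(0.9 + 0.1 × 2) = 0.1186.
- Complete-case risk = (0.08 + 0.828 × 0.1186)/0.908 = 19.6%.
- Risk by the product form of Kaplan-Meier (inpatient survival times traced post-discharge survival) = 1 − 0.92 × (1 − 0.1186) = 18.9%.

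Both are below the true 20%. When the untraced die at the traced rate, the product form returns 20.0%.

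**The other possible denominator.** Counting the untraced as alive gives I + P(1 − u): 19.0–19.5% at 10% untraced and 18.0–19.0% at 20%. The null ratio for 15% against 5% untraced is then 0.185/0.195 = 0.95 or 0.1925/0.1975 = 0.97.

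**Bounds.** With u = 0.10 and the untraced dying at the traced rate, setting all the untraced alive or all dead gives 19.0% to 28.0% (I = 0.10) or 19.5% to 28.0% (I = 0.15).

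**The case against.** **Exclusion is inferred.** The SAP gives no denominator here, and Analysis populations speaks of including everyone randomised. Recorded deaths over all enrolled is not ruled out. This is fair. But a GLM with unimputed missing outcomes does drop them, and the alternative is biased downward. Without a rule, the choice could be made after the data are seen.

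**Direction.** A reader might infer that the reported risk is too high whenever anyone is lost. The documents do not support that. The sign depends on the death risk of the untraced, and nothing in the SAP excludes death itself making next of kin harder to reach. Nor did everyone untraced necessarily leave hospital alive: the follow-up section says only that this is usual, and it allows for withdrawal.

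**Size and rank.** The item is one of the other outcomes. With 306 per arm and 20% risk, the standard error of each proportion is √(0.2 × 0.8/306) = 2.3 points. The 95% interval around a ratio of 1 is about 0.73–1.37, ignoring clustering. The shifts shown lie inside that. This stands and limits the severity, although random error does not cancel a systematic shift.

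**Already disclosed.** The CONSORT diagram will show losses, and missing outcomes will be reported. That discloses the problem without correcting the estimate.

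**Kaplan-Meier is not clean.** It assumes non-informative censoring. With staggered discharges, people censored at discharge are represented by all still at risk, including inpatients, so some bias can remain. The SAP also means this item to complement the time-to-event analysis. Both points stand, and they are reasons to keep the GLM alongside and to add bounds.

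**Conclusion.** The point holds in a limited form. Followed as written, the analysis keeps inpatient deaths and drops mainly people discharged alive, so it conditions on part of the outcome.

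The bias is likely upward: about 1 point at 10% untraced and 2 to 3 points at 20%, against a true 20%. The null risk ratio is about 1.05–1.07 if 5% and 15% are untraced by arm. These figures assume 10–15% inpatient deaths, loss only after discharge, and the same post-discharge death rate in traced and untraced. The bias disappears or reverses if the untraced die much more often, and equal tracing leaves the null ratio at 1.00.

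A reader might also infer that the trial's main mortality comparison is compromised. It is not: the secondary Cox analysis censors at last known alive, and inpatient mortality does not depend on tracing. The change is worth making before the data are analysed, but nothing in the primary analysis depends on it.

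**What to change.** In Analysis methods, item 6:

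1. Report the 56-day risk of death in each arm as 1 minus the Kaplan-Meier estimate at day 56, using the censoring times in Withdrawal / follow up. Give the risk ratio and risk difference with a bootstrap interval that resamples admission days.
2. Keep the log-binomial GLM as a named complete-case sensitivity analysis, and state its denominator.
3. Show the number with unknown day-56 status by arm beside both results.
4. Add best-case and worst-case bounds for those participants, including opposite assumptions in the two arms.
5. Reconcile how deaths are ascertained: the time-to-event entry in Outcome definitions includes home visits when the phone fails, while the entry for the proportion names only the phone call.

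The cost is SAP wording and a few lines of code, with no new data. The downside is a bootstrap interval and a remaining assumption of non-informative censoring after discharge. If the untraced die more often, Kaplan-Meier is too low, which is why the bounds belong with it.
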